Comparison of Effects of Peripheral Nerve Block and Topiramate in the Treatment of Medication Overuse Headaches

07.07.2019

Purpose

In this study, we compared the effectiveness of peripheral nerve block (greater occipital nerve block with supraorbital nerve block) versus topiramate as detoxification therapies in chronic migraine patients with medication overuse headache.

Methods

Ninety chronic migraine patients with medication overuse headache were included in this study. Patients divided into the two groups. The first group received topiramate and the second group received nerve block as detoxification therapy. Patients' records regarding the VAS scores and headache frequencies were collected before and after the therapy. Comparisons regarding VAS scores, headache frequencies, 50% responder rates and 75% responder rates were performed in between topiramate and nerve block groups.

Data collection

The study was carried on by 2 neurologists. The first neurologist obtained the data regarding the migraine features from each patient included. Each patient kept a diary documenting frequency, visual analog scale (VAS) as the number of headache attacks in the preceding 4 weeks. At the end of the fourth week, forms were collected by first neurologist and patients were referred the second neurologist for treatment regimens were to be introduced. Detoxification process was maintained in the inpatient clinic for ten days and preventive treatment was started simultaneously by

the second neurologist. After discharge, new forms were delivered and collected by the first neurologist after 4 weeks. All patients were informed about possible adverse reactions and those caused discontinuation of therapy were noted.

Statistical analysis

Normality of distribution was assessed with the D'Agostino-Pearson test. Continuous variables with a normal distribution were assessed in two or more groups using the Student's t-test. Mann Whitney U was utilized to compare the data that were not normally distributed. Nominal categorical data were assessed using the chisquare test. The pre- and post-treatment comparison of normally and non-normally distributed data were undertaken using the paired t-test and the Wilcoxon test, respectively. A two-tailed p value of <0.05 was considered statistically significant.

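### No named between-group test uses baseline VAS or headache frequency as a covariate, although both were collected before treatment, and the plan leaves open whether post-treatment values or changes are compared

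*Combined protocol and SAP*

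**What the plan says.** The Methods section puts the total at 90 patients and describes allocation only as "Patients divided into the two groups". It states that "records regarding the VAS scores and headache frequencies were collected before and after the therapy", and lists what is compared between the arms: "Comparisons regarding VAS scores, headache frequencies, 50% responder rates and 75% responder rates were performed in between topiramate and nerve block groups". It does not say whether the VAS and frequency comparisons use the post-treatment value or the change from baseline, and it does not define the responder percentages.

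The Data collection section places the first four-week diary before treatment: at the end of that period "forms were collected by first neurologist and patients were referred the second neurologist for treatment regimens were to be introduced".

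The Statistical analysis section gives Student's t-test for normally distributed continuous variables, states that "Mann Whitney U was utilized to compare the data that were not normally distributed", and assigns chi-square to categorical data. The tests that explicitly use baseline are kept for a different question: "The pre- and post-treatment comparison of normally and non-normally distributed data were undertaken using the paired t-test and the Wilcoxon test, respectively". Significance is two-sided at 0.05. No section contains a regression or covariance model.

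**The concern.** Each patient has a pre-treatment value of the same quantity that is later compared between arms. Such a value usually predicts the later one, so leaving it out of the model can waste information in a trial of only 90 patients. The paired and Wilcoxon tests do not fill the gap, because they describe movement over time and do not contrast topiramate with nerve block.

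The unspecified outcome adds a second problem. When the arms differ at baseline, even by chance, comparing post-treatment values and comparing changes err in opposite directions. The plan has no rule for which result counts. A baseline-adjusted analysis, named as the one to be relied on, would close that choice.

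**Working it through.** **Inputs from the document.** Total 90 (Methods); two-sided 0.05 (Statistical analysis). The plan gives no SD, correlation, effect size, arm sizes or power, so there is no stated figure to reproduce.

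**Assumptions, for illustration.** 45 per arm, complete data, normal outcomes, equal SD before and after (set to 1), true difference 0.5 SD, baseline-to-post correlation ρ of 0.3, 0.5 or 0.7.

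**Step 1: standard error.** √(2/45) = 0.2108 SD for a difference in post-treatment means.

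**Step 2: effective SD.** Post-values: 1. Change: √(2 − 2ρ). ANCOVA: √(1 − ρ²).

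**Step 3: power.** Noncentrality = 0.5 / (0.2108 × effective SD), with the noncentral t on 88 df (87 for ANCOVA).

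| ρ | Post: noncentrality, power | Change: SD, noncentrality, power | ANCOVA: SD, noncentrality, power |
|---|---|---|---|
| 0.3 | 2.372, 65.0% | 1.183, 2.004, 50.9% | 0.954, 2.486, 69.1% |
| 0.5 | 2.372, 65.0% | 1.000, 2.372, 65.0% | 0.866, 2.739, 77.3% |
| 0.7 | 2.372, 65.0% | 0.775, 3.062, 85.7% | 0.714, 3.321, 90.7% |

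Rounded, ANCOVA gains 4, 12 and 26 points over post-values and 18, 12 and 5 over change. In sample-size terms, 90 patients with ANCOVA match 90/(1 − ρ²) = 99, 120 and 176 on post-values.

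**Step 4: chance imbalance under randomisation.** The baseline difference also has SE 0.2108 SD, so its 95% range is ±1.96 × 0.2108 = ±0.41 SD. A gap above 0.3 SD occurs in 15.5% of such trials and above 0.5 SD in 1.8%. Given a gap of 0.41 SD, the post-value contrast is shifted by ρ × 0.41 = 0.12 to 0.29 SD. The change contrast is shifted by (1 − ρ) × 0.41 = 0.29 to 0.12 SD in the opposite direction. The false-positive rate conditional on that gap is about 8–20% on post-values and 10–16% on change.

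**Step 5: skewed counts.** Headache frequency may be far from normal. Poisson counts with log-normal frailty were simulated: assumed means 15 before and 7 after, 25% reduction, skewness 1.3 to 2.7, 8,000 trials per setting.

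| Observed correlation | Mann-Whitney on post-values | ANCOVA with HC3 |
|---|---|---|
| 0.48 | 53% | 64% |
| 0.55 | 42% | 55% |
| 0.37 | 34% | 35% |

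With no true effect, HC3 ANCOVA rejected in 4.4–4.6% of trials. The gain disappears in the last setting.

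**Step 6: if allocation was not random.** No true effect, assumed imbalance 0.3 SD, ρ 0.5 to 0.7, nominal 5%:

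| Source of imbalance | Post-values | Change | ANCOVA |
|---|---|---|---|
| Regresses to a common mean | 11–17% | 8–11% | about 5% |
| Stable severity, measured with error | 29% | about 5% | 9–13% |

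No single analysis is safe under both mechanisms, which is why ANCOVA and change scores would be needed together. None of these figures describes the responder rates.

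**The case against.** The strongest reply is that nothing is broken. The named tests are conventional and, under random allocation, valid; preferring ANCOVA is a design choice. The size of the gain rests entirely on inputs that the document does not supply, and one plausible setting shows almost none. This stands, and it limits the point to a cheap improvement.

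A reader might infer that the between-group comparisons ignore baseline altogether. The text does not support that. If changes are compared, baseline enters by subtraction, and the responder rates may be defined against each patient's own baseline. Only the absence of baseline as a covariate is established.

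A reader might also infer that patients were not randomised. The document is silent, and silence does not show non-random allocation. Step 6 is therefore conditional.

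Two further objections stand and shape the fix. The text is in the past tense, so analysis may be complete; demoting tests already run would then be a data-informed change. Replacing Mann-Whitney with linear ANCOVA also moves the target from a rank comparison to a mean difference, which must be stated.

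Finally, the illustration assumes that all 90 patients are analysable. The Data collection section notes discontinuations for adverse reactions but gives no rule for their post-treatment data, so real power could be lower for every method.

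**Conclusion.** The point holds as a cheap improvement. It is certain from the text that no named between-group test for VAS or headache frequency has a baseline covariate, that both baselines precede treatment, and that the choice between post-treatment values and changes is open. The size of the benefit is uncertain: under the normal-data assumptions above it is 4 to 26 points of power over post-values, and about nil for very skewed, weakly correlated counts.

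The documents do not support calling the named tests invalid or the allocation non-random. The allocation method and the responder definitions are needed to interpret the results, but their absence is a reporting gap and not the basis of this point.

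**What to change.** 1. Compare post-treatment VAS and post-treatment headache frequency between arms, each by linear ANCOVA on group and that outcome's own baseline, with HC3 standard errors. Report the Student's t or Mann-Whitney result beside it, and state whether that test uses post-treatment values or changes.
2. If the data are not yet analysed, make ANCOVA the lead analysis. If they are, label it post hoc and leave the original tests as reported.
3. State that ANCOVA estimates a mean difference, also for skewed data where the existing plan would make a rank comparison.
4. State how patients were divided. If not at random, give the change-score analysis beside ANCOVA, report any disagreement as unresolved, and word the conclusion as an adjusted association subject to unmeasured confounding.
5. For interpretation, say what the 50% and 75% responder rates are measured against.

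The cost is two models and a short paragraph, with no new data; if allocation was not random, add a change-score analysis and a more modest conclusion. The drawbacks are the changed target for skewed outcomes and a gain that depends on an unstated correlation.

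### The plan does not say how, when or by whom patients were assigned to topiramate or nerve block, and its unadjusted tests cannot separate a treatment effect from selection

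*Combined protocol and SAP*

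**What the plan says.** The Purpose section sets out a comparison of effectiveness between the two treatments. Methods gives the sample, "Ninety chronic migraine patients with medication overuse headache were included in this study", then the allocation, "Patients divided into the two groups", then the arms: "The first group received topiramate and the second group received nerve block as detoxification therapy". Arm sizes and the allocation ratio are not stated.

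Data collection describes the patient's path in some detail. The first neurologist records migraine features, and the patient keeps a four-week diary of headache frequency and VAS. The first neurologist then collects the forms, and "patients were referred the second neurologist for treatment regimens were to be introduced". Treatment starts in the inpatient clinic under the second neurologist. For follow-up, "After discharge, new forms were delivered and collected by the first neurologist after 4 weeks".

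Statistical analysis lists Student's t-test, Mann-Whitney U and chi-square for comparisons between groups, and paired tests for change within a group. No covariate adjustment is mentioned. On the significance level it says "A two-tailed p value of <0.05 was considered statistically significant".

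**The concern.** A two-sample test answers a question about treatment only if the arms would have had the same expected outcome without any difference in treatment. Random, concealed assignment secures that. Here nothing in the text does: the workflow says who hands out and collects each form, yet contains no step at which the arm is decided.

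The two options are an injection procedure and an oral drug, so there are obvious grounds on which a choice could be made: dislike of needles, earlier drug failure, the drug overused, mood. Any of these may be related to outcome. If they influenced who received what, the planned tests would count the resulting imbalance as treatment effect. The error could go either way: selection could create a difference where there is none, or hide a real one. At stake is whether the stated Purpose can be met at all.

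**Working it through.** **Step 1: reading the text.** Four things would let a reader judge the allocation.

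| Item | What the document gives |
|---|---|
| Method (random sequence or other rule) | Only that patients were divided |
| Who assigned the arm | Not stated |
| When, relative to the baseline diary | Not stated |
| Concealment until assignment | Not stated |

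The sentence on division follows directly after the one on inclusion, but that does not fix its timing. The second neurologist introduces the regimen. Introducing a regimen is not the same as choosing it, and the text says only the former.

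**Step 2: could the planned analysis compensate?** The t-test, Mann-Whitney U and chi-square test use only the outcome and the arm. None uses baseline VAS, baseline headache frequency or the recorded migraine features, so none would correct an imbalance in them.

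**Step 3: how large could the effect be?** The document gives no power calculation, effect size, SD or response rate, so there is no figure of its own to reproduce. What follows is an illustration.

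From the document: 90 patients in total, two-sided 5% level, a 50% responder rate as one of the outcomes.

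Assumed: 45 per arm; no true treatment effect; half of all patients of good prognosis; 50% response in 60% of good-prognosis and 30% of poor-prognosis patients; the degree of imbalance.

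With f the share of good-prognosis patients in an arm:

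- Response rate in the arm: p = 0.60f + 0.30(1 − f)
- SE = √{[p₁(1 − p₁) + p₂(1 − p₂)] / 45}
- Rejection probability = Φ(d/SE − 1.96) + Φ(−d/SE − 1.96), with d = p₁ − p₂

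| f in the two arms | p₁ v p₂ | d | SE | d/SE | Rejection probability |
|---|---|---|---|---|---|
| 0.50 / 0.50 | 45% v 45% | 0 | 0.105 | 0 | 5.0% |
| 0.60 / 0.40 | 48% v 42% | 6 points | 0.105 | 0.573 | 8.8% |
| 0.65 / 0.35 | 49.5% v 40.5% | 9 points | 0.104 | 0.862 | 13.8% |
| 0.80 / 0.20 | 54% v 36% | 18 points | 0.103 | 1.745 | 41.5% |

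For the second row, Φ(0.573 − 1.96) + Φ(−0.573 − 1.96) = 0.083 + 0.006 = 0.088. If the critical value is set with the pooled variance, as in a chi-square test, the last three rows become 8.8%, 13.7% and 40.2%.

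**Step 4: the same question on a continuous scale.** With 45 per arm, SE = √(2/45) = 0.211 SD. A prognostic gap of b SD caused by selection alone, put into the same formula with d/SE = b/0.211, gives 7.6% for b = 0.1, 15.8% for 0.2, 29.6% for 0.3 and 66.0% for 0.5. If the 90 patients were split 30/60, the values for 0.2 and 0.5 would be 14.5% and 60.9%, so the assumption of equal arms matters little.

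**The case against.** The strongest reply is that this is silence and not evidence of a fault. The sentence on division names no actor, time or rule. Patients could have been randomised, or assigned at inclusion, or assigned by a third party, and the fact left out. That stands. A reader might infer from the workflow that the second neurologist picked the regimen after seeing the patient and the diary. The document does not support this: it says who introduced the treatment, not who decided on it, and it does not say that the second neurologist saw the diaries.

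A second reply concerns what adjustment could do. A reader might infer that the possible grounds for choice were never recorded, so that no analysis could help. That is too absolute. The first neurologist recorded migraine features whose content is not listed; the drug overused and earlier drug failure could be among them. Adjustment for what was recorded might reduce bias. It could not be relied on to remove bias from grounds that were not recorded, and the plan specifies no adjustment in any case.

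Third, the text is in the past tense throughout, so allocation may be over and advice to randomise may come too late. This also stands, and it determines the order of the remedies.

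Fourth, the numbers are hypothetical. They are: the mildest imbalance shown takes the error only from 5% to about 9%, and nothing in the document points to an imbalance as large as 80/20.

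None of these replies supplies the missing assignment step. Only a statement that assignment was random and concealed would answer the point.

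**Conclusion.** The point holds as a gap in the plan that bears directly on its Purpose. The document does not state how, when or by whom arms were assigned, it describes no random or concealed step, and its between-group tests are unadjusted. Followed as written, it does not support reading a difference between arms as a difference in effectiveness. It does not establish that allocation was non-random or that any bias occurred.

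The false-positive range of about 9% to 41% shows only that moderate to strong selection would matter in a study of this size. It rests wholly on the assumed response rates, imbalances and 45 patients per arm. The conclusion about the plan does not depend on it.

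**What to change.** **If allocation is over, as the past tense suggests:** state how, when and by whom each patient's arm was assigned, and whether the assignment was concealed until then. If it was random and concealed, that statement resolves the point.

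**If assignment was not random:** describe the study as a non-randomised comparison. Make the primary between-group analysis one adjusted for baseline VAS, baseline headache frequency and the recorded migraine features, for example a regression model with these as covariates. Limit the conclusion to association, because unrecorded grounds for choice cannot be adjusted away.

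**If any allocation is still open:** assign from a computer-generated random list prepared in advance and held by someone who neither recruits nor treats. Open each assignment only after the first neurologist has collected the baseline form. The existing division of work between the two neurologists accommodates this.

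**Cost:** for completed allocation, a few sentences, one adjusted analysis of data already collected and, if assignment was not random, a weaker conclusion. For open allocation, a random list with sealed assignments for the remaining patients, and loss of clinician choice of regimen for them.

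### Four between-group effectiveness outcomes are each tested at 0.05 with no primary outcome, order or adjustment; with comparable arms and no true difference, at least one is significant in about 7–17% of simulated trials

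*Combined protocol and SAP*

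**What the plan says.** The Purpose section asks one question, in the words "we compared the effectiveness of peripheral nerve block", with topiramate as the comparator.

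The Methods section gives the total, "Ninety chronic migraine patients with medication overuse headache were included in this study", and says only "Patients divided into the two groups". It gives neither the arm sizes nor the method of allocation. It then lists the outcomes together: "Comparisons regarding VAS scores, headache frequencies, 50% responder rates and 75% responder rates were performed in between topiramate and nerve block groups".

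The Statistical analysis section chooses the test by the distribution of the data, checked with a D'Agostino-Pearson test. Normal continuous outcomes go to a t-test; for the rest, "Mann Whitney U was utilized to compare the data that were not normally distributed". Categorical outcomes go to a chi-square test, with no word on continuity correction. One threshold covers everything: "A two-tailed p value of <0.05 was considered statistically significant".

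The document does not name a primary outcome, a testing order or a multiplicity adjustment, and it has no sample-size calculation from which a primary outcome could be inferred. It does not say whether a responder is defined on headache frequency or on VAS, or whether VAS and frequency are compared as post-treatment values or as changes.

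**The concern.** There is one effectiveness question and four tests that can answer it, each with its own 5% chance of a false difference. The plan has no rule for turning four p-values into one conclusion. It does not say that any single significant result will be read as superiority, but nothing in it prevents that. On that reading the 0.05 threshold limits the error of each test, not of the effectiveness conclusion.

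There is also a problem that needs no percentage. If, say, the 75% responder rate favours one therapy and headache frequency shows no difference, the plan does not say which result decides. The undefined responder measure and the unstated choice between post-treatment values and changes leave further room, because even the number of tests is not fixed.

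**Working it through.** **Plan's own figure.** None. The document states no power, no sample-size derivation and no familywise error rate.

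**Inputs from the document.** 90 patients (Methods); four between-group outcomes (Methods); two-sided 0.05 for each, t-test or Mann-Whitney for continuous data, chi-square for categorical data (Statistical analysis).

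**Assumptions, not in the document.** Comparable arms and no true difference; arms of 45/45 or 30/60; one test per outcome; frequency and VAS reductions bivariate normal with correlation 0, 0.3, 0.5, 0.7, 0.9 or 1; both responder rates are nested cut-offs on frequency, with 50%/75% responder rates of 30/10, 50/20, 60/30 or 70/40%; chi-square with and without continuity correction.

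**Step 1: reference value.** Four independent tests would give 1 − (1 − 0.05)^4 = 1 − 0.8145 = 18.5%. The outcomes here are correlated, so this is only a landmark. Nor is 4 × 0.05 = 20% a firm ceiling. That bound needs exactly four tests that each hold 5%. At 45/45 with 30/10% rates, the uncorrected chi-square for the 75% responder rate alone rejects in 5.8–6.1% of null trials, and the four individual rates sum to 21.0–21.5%.

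**Step 2: null simulation.** Chance that the smallest of the four p-values is below 0.05, with 40,000 replicates per setting. The Monte Carlo standard error at 15% is √(0.15 × 0.85 / 40,000) = 0.0018.

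| Continuous test, arms, correlation | Chi-square uncorrected | Continuity-corrected |
|---|---|---|
| t-test, 45/45, 0 to 0.9 | 12.3–16.8% | 9.3–12.4% |
| t-test, 45/45, 1 | 10.9–12.7% | 7.5–8.0% |
| t-test, 30/60, 0 to 0.9 | 12.0–15.5% | 9.1–12.5% |
| t-test, 30/60, 1 | 10.6–11.0% | 7.4–7.9% |
| Mann-Whitney, 45/45, 0 to 1 | 10.5–16.7% | 7.2–12.2% |
| Mann-Whitney, 30/60, 0 to 1 | 10.2–15.5% | 7.3–12.2% |

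The frequency t-test alone rejects in 4.8–5.3%. The low end needs perfect correlation and the continuity correction; the high end needs weak correlation and no correction.

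**Step 3: sensitivity.** A different model, with pre- and post-treatment values and the D'Agostino-Pearson choice of test built in, gave about 9% to 17.7%. Defining responders on VAS gave about 16%. A wider grid of responder rates reached down to 6.2% (rates 10/2%, correlation 1, corrected). No setting fell to 5%.

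**Step 4: effect of Holm.** Holm's first step is 0.05 / 4 = 0.0125, so under no difference any rejection requires the smallest p-value to be below 0.0125. That happened in 1.7–4.3% of trials over all the settings of Step 2.

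**Step 5: cost in power.** The detectable difference in SD units is approximately (z for alpha + z for power) × √(1/n1 + 1/n2).

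- 45/45: √(2/45) = 0.211. At 0.05, (1.960 + 0.842) × 0.211 = 0.59; at 0.0125, (2.498 + 0.842) × 0.211 = 0.70. The exact t calculation gives 0.597 and 0.717.
- 30/60: √(1/30 + 1/60) = 0.224. The same formula gives 0.63 and 0.75; exact 0.633 and 0.760.
- Power at 0.0125 for an effect with 80% power at 0.05: Φ(2.802 − 2.498) = Φ(0.304) = 62%; exact 61.2%.

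**The case against.** The strongest reply is that the percentage is not a property of this plan. Arm sizes, correlation, responder rates, the responder measure and the continuity correction are all assumed, and the answer runs from close to nominal to more than three times nominal. That is right. The figures show a range under stated conditions and should not be quoted as the trial's error rate.

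A second reply is that inflation arises only if any one significant result is taken to show greater effectiveness, and the plan states no such rule. If all four results are reported side by side, each p-value keeps its own meaning. This is fair, but it leaves the effectiveness question without a deciding result, which is itself the gap.

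Third, comparable arms may be the larger problem. The document says only that patients were divided into groups, and if the arms are not comparable neither these figures nor Holm protects a treatment claim. That stands as a separate weakness; resolving it would not resolve this one.

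Finally, Holm takes no account of the overlap between the two responder rates, so it brings the error below 5% at a cost in power, and if adopted after results are known it is itself post hoc. Both points stand as costs to disclose. They do not make the adjustment unsound.

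**Conclusion.** The concern holds. The omission is clear from the text: four outcomes of equal standing, one 0.05 threshold, and no primary outcome, order or adjustment. If any one significant test may carry the conclusion, the chance of a false difference is about 7–17% instead of 5%. This is conditional on comparable arms, one test per outcome and the assumed correlations and responder rates. Its exact size is uncertain, but its direction is not. The within-group pre/post tests are not counted. The plan should be changed, because the gap affects how the headline result is read, though not the data collected.

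**What to change.** The text is in the past tense, so the first case is that outcomes have already been compared.

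- **Already compared.** Apply Holm across the four between-group tests (thresholds 0.0125, 0.0167, 0.025 and 0.05 for the ordered p-values) and say that the adjustment was added afterwards. Label any newly chosen primary outcome post hoc. Report each between-group difference with a 95% confidence interval. This means re-ranking four existing p-values and adding intervals; no new data are needed.
- **Not yet compared.** Name one primary outcome, for example headache frequency from the 4-week post-discharge diary, tested at two-sided 0.05. Test the other three only if it is significant, by fixed sequence or Holm, or report them as descriptive. Give 95% confidence intervals for all four. This is one paragraph of SAP wording.
- **In both cases.** State the one measure on which both responder rates are based, and whether VAS and frequency are compared as post-treatment values or as changes, so that the number of tests is fixed.

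The price is that a lone nominally significant outcome can no longer carry the headline claim. Under Holm, power for an effect of 0.60 SD at 45/45 (0.63 SD at 30/60) falls from 80% to 61% at the strictest step, where 80% power needs 0.72 SD (0.76 SD).

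### Does the lack of a stated analysis set, responder denominator and missing-form rule make the group comparison wrong?

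*Combined protocol and SAP*

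**What the plan says.** The Methods section gives the cohort as "Ninety chronic migraine patients with medication overuse headache were included in this study" and the allocation as "Patients divided into the two groups". It does not say whether the ninety are everyone who entered or only those with complete data, and it gives no arm sizes. It lists the outcomes: "Comparisons regarding VAS scores, headache frequencies, 50% responder rates and 75% responder rates were performed in between topiramate and nerve block groups".

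Under Data collection there are two forms per patient. For the pre-treatment diary, "At the end of the fourth week, forms were collected by first neurologist". For follow-up, "After discharge, new forms were delivered and collected by the first neurologist after 4 weeks". The only sentence on stopping treatment is "All patients were informed about possible adverse reactions and those caused discontinuation of therapy were noted".

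Under Statistical analysis, the within-group tests are set out as "The pre- and post-treatment comparison of normally and non-normally distributed data were undertaken using the paired t-test and the Wilcoxon test, respectively", and responder rates would fall under "Nominal categorical data were assessed using the chisquare test". No section names an analysis population, a responder denominator, or a way of handling an absent second form.

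**The concern.** Every post-treatment value comes from a single form. A paired t-test or Wilcoxon test needs both values from each patient, and a percentage fall cannot be computed without the second. If nothing is imputed, patients without that form drop out of the paired tests, and they may drop out of the responder rates too.

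The two treatments are a drug and an injection procedure, so equal form return cannot be taken for granted. If one arm lost more patients, and those patients did worse, the remaining patients in that arm would look better than the whole arm. Two equally effective treatments could then appear different, or a real difference could shrink. A reader would have no stated rule by which to tell.

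**Working it through.** The plan has no figure of its own to reproduce: it gives 90 patients without power, effect size or dropout allowance.

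**Inputs.** From the documents: 90 patients, two groups, chi-square test, two-sided 0.05. Assumed: 45 per arm, response r = 50% in both arms, loss d, and response q among lost patients. The false-positive rates come from simulation (400,000 replicates, binomial loss, uncorrected chi-square).

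**Formulas.** Response among patients with both forms is (r − d·q)/(1 − d). Response with missing counted as non-response, over all patients, is r − d·q.

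**Loss of 20% against 5%.**

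| q | Completer rates | Gap (points) | Completer false positives | Missing = non-response rates | Gap (points) | False positives |
|---|---|---|---|---|---|---|
| 0% | 62.5% v 52.6% | +9.9 | 14% | 50.0% v 50.0% | 0 | 4.5% |
| 25% | 56.3% v 51.3% | +4.9 | 7% | 45.0% v 48.8% | −3.8 | 6% |
| 50% | 50.0% v 50.0% | 0 | 5% | 40.0% v 47.5% | −7.5 | 10% |
| 75% | 43.8% v 48.7% | −4.9 | 7% | 35.0% v 46.3% | −11.3 | 19% |

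A positive gap favours the arm with more loss. For example, at q = 0 the completer rates are 0.50/0.80 = 0.625 and 0.50/0.95 = 0.526. At q = 100% the completer gap is 0.30/0.80 − 0.45/0.95 = −9.9 points.

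**Other loss patterns.**
- 5% against 0%, q = 0: completer false-positive rate 5.7%.
- 10% against 0%, q = 0: 8%.
- 20% against 0%: the completer rate is 20% at q = 0 and 5% at q = 50%. Missing as non-response gives 4.5% and 15%.
- 20% in both arms, same q in both: about 5%.
- 20% in both arms, q = 0% in one and 50% in the other: 0.50/0.80 = 62.5% against (0.50 − 0.10)/0.80 = 50.0%, a 12.5-point gap with 19% false positives. Equal loss is therefore no guarantee of a fair comparison.

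**A real difference.** Take 40% against 60%, loss of 20% in the worse arm and 5% in the better, q = 0. The completer gap is 0.60/0.95 − 0.40/0.80 = 13.2 points, against 20 for all patients. Power is 22% against 46%.

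**One concrete data set.** Each arm has 22 responders of 45, with 9 and 1 forms missing, all from non-responders. Completers give 22/36 = 61.1% and 22/44 = 50.0% (p = 0.32). All patients give 22/45 = 48.9% in both.

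**Within-group falls.** If lost patients did not change at all, the completer mean fall in VAS or frequency is overstated by 1/(1 − 0.10) = 1.11 at 10% loss and 1/(1 − 0.20) = 1.25 at 20%. This distorts each arm's own change. The paired tests do not compare the arms, so this restriction on them cannot favour one treatment over the other.

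**The case for a change.** The strongest case for acting is that the text is silent where two honest analysts could diverge. In the data set above, one could report 61% and the other 49% for the same arm, both consistent with the plan. The plan foresees that adverse reactions may end treatment, the mechanism of bias is sound, and the figures reproduce. Writing down a denominator costs a few sentences.

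Much of this stands. The omission is certain, and neither redaction nor the reading of the PDF explains it. The range of answers under heavy, outcome-related loss is wide.

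Three things weaken the case. First, the documents never say that a form was missing. Stopping treatment is not the same as failing to return a diary, and the text does not exclude those who stopped. Second, a completer denominator for the responder rates is an inference: the text equally allows all patients in the denominator. Third, the natural remedy, a missing form counted as non-response, does better only when lost patients respond poorly. Where they respond about as well as the rest, it adds an error that the completer test does not have. Choosing it as the main rule is a judgement that the documents give no data to settle.

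**Conclusion.** No change to the plan follows. The text leaves out the analysis set, the responder denominator and the handling of an absent follow-up form, but it states no rule that yields a wrong result.

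The possible distortion runs from nothing to about 10 points either way at 20% against 5% loss, with a completer false-positive rate between 5% and 14%. At 5% against 0% loss it is negligible. All of this rests on assumed arm sizes, response rates and losses, because the documents give none. If all ninety forms came back, the question does not arise. If the ninety are only those with complete data, no form is missing among them, though selection before inclusion would remain possible.

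This is a gap of the kind that an analyst fills at the reporting stage. Patients entered, treatment discontinuations and forms returned are counted by group. Responder rates are given for patients with both forms and for all patients, and any disagreement between the two is read as dependence on the missing forms. The document is written in the past tense, so a rule inserted now would not be prespecified, and no single rule is better across the plausible cases.
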